7.1. Adverse Events

The analysis of AEs is based on the medical dictionary for regulatory activities (MedDRA) coded terms as provided in the clinical database. All reported AEs (solicited local, solicited systemic, and unsolicited) during the vaccination periods (Post-dose 1 and Post-dose 2) (ie, AEs following vaccination and AEs that have worsened since baseline) will be included in the analysis. Listings of AEs will include all reported AEs.

Note that the AEs include any occurrence that is new in onset or aggravated in severity, toxicity grade or frequency from the baseline condition, or clinically relevant abnormal results of diagnostic procedures, including clinically relevant laboratory test abnormalities.

7.1.1. Definitions

Solicited AEs are precisely defined events (local and systemic) that subjects are specifically asked about and which are noted by subjects in the diary. All other AEs are considered unsolicited. Refer to Sections 9.3 and 12.1.1 of the CTP¹ for further details.

Solicited Local (Injection Site) Reactions

The analysis of local solicited AEs will include:

- Pain/Tenderness
- Erythema
- Induration/Swelling
- Itching

Solicited Systemic Adverse Events

The analysis of systemic solicited AEs will include:

- Fever (defined as body temperature of 38°C or higher)
- Headache
- Fatigue/Malaise
- Myalgia

- Nausea/Vomiting
- Arthralgia
- Chills

Serious Adverse Events

SAEs will be collected from signing of the ICF until the end of the study. An SAE based on the International Council for Harmonisation (ICH) and the European Union (EU) Guidelines on Pharmacovigilance for Medicinal Products for Human Use is any untoward medical occurrence that at any dose:

- Results in death
- Is life-threatening (the subject was at risk of death at the time of the event. It does not refer to an event that hypothetically might have caused death if it were more severe.)
- Requires inpatient hospitalization or prolongation of existing hospitalization
- Results in persistent or significant disability/incapacity
- Is a congenital anomaly/birth defect
- Is a suspected transmission of any infectious agent via a medicinal product
- Is medically important*.

*Medical and scientific judgment should be exercised in deciding whether expedited reporting is also appropriate in other situations, such as important medical events that may not be immediately life-threatening or result in death or hospitalization but may jeopardize the subject or may require intervention to prevent one of the other outcomes listed in the definition above. These should usually be considered serious.

Immediate Reportable Events

The following list of neuroinflammatory disorders are categorized as IRE, and should be reported to the sponsor within 24 hours after becoming aware of the event using the IRE Form. Relevant data from the IRE form will be captured in the clinical database.

- Cranial nerve disorders, including paralyzes/paresis (eg, Bell's palsy)
- Optic neuritis
- Multiple sclerosis
- Transverse myelitis
- Guillain-Barré syndrome, including Miller Fisher syndrome, Bickerstaff's encephalitis and other variants
- Acute disseminated encephalomyelitis, including site specific variants: eg, non-infectious encephalitis, encephalomyelitis, myelitis, myeloradiculomyelitis
- Myasthenia gravis and Lambert-Eaton myasthenic syndrome

- Immune-mediated peripheral neuropathies and plexopathies (including chronic inflammatory demyelinating polyneuropathy, multifocal motor neuropathy and polyneuropathies associated with monoclonal gammopathy)
- Narcolepsy
- Isolated paresthesia of >7 days duration

Causality

The solicited local AEs will be considered as related to the study vaccine, by definition. An unsolicited and solicited systemic AEs will be considered related to the use of the study vaccine if the attribution is possible, probable or very likely. An AE will be considered not related with the use of the study vaccine if the attribution is not related or doubtful. Refer to Section 12.1.2 of the CTP¹, for further details.

Severity Criteria

The severity of the AEs is classified by the investigator as mild, moderate or severe using the Division of Microbiology and Infectious Diseases (DMID) Toxicity Table for Use in Trials Enrolling Healthy Adults (Attachment 3).

Solicited events that are graded less than mild, are not considered AEs. For some solicited events (eg, induration/swelling), the diameter and grading (as reported by the investigator [ie, functional grade]) are collected in the electronic case report form (eCRF). The diameter will be used to derive the toxicity grading. The worst grade should be used when both the diameter derived grade and the functional grade are available. If only the functional grade is available, then this should be used

7.1.2. Data Handling Rules

Missing data will not be imputed. If severity or relationship of AEs to the study vaccine could not be derived (ie, missing or unknown), it will be considered as unknown, for analysis purposes. Local solicited AEs will be considered as related with the use of the study vaccine, by definition.

Solicited events will always be allocated to the analysis period (Section 2.1). For analysis purpose, the AEs will be allocated to periods and/or phases as described in Attachment 2.1.

7.1.3. Analysis Methods

In general, the AEs following vaccination will be summarized (ie, tables of descriptive statistics) by vaccination schedule and presented per period/phase. Similar summary tables will also be provided pooled by vaccine (dose).

Furthermore, unsolicited AEs will be summarized (showing number and percentage) by System Organ Class (SOC) and Preferred Term (PT). Solicited AEs (recorded by day) will be converted into the analysis format of unsolicited AEs (recorded by event), as detailed in Attachment 2. These solicited AEs will be summarized by class (local, systemic) and Preferred Term. For

solicited as well as unsolicited AEs, tables focusing on severity will be created. Focus will also be on the relationship (to the study vaccine) of the solicited systemic and unsolicited AEs.

The SAEs, AEs with fatal outcome, AEs leading to permanent stop of study vaccination, Grade 3 AEs and IREs will also be listed. A table summarizing all those parameters will further be created and presented per analysis period and vaccination schedule. Summary tabulations by SOC and PT for each of the category of events (ie, SAEs, AEs with fatal outcome, AEs leading to permanent stop of study vaccination, Grade 3 AEs and immediate reportable events) will also be generated on the entire reporting period. Subject narratives will be generated for these events, except Grade 3 AEs.

For the most frequent (at least 10% of subjects in any vaccination schedule) solicited local and systemic AEs, the duration and time to first onset of the events will also be summarized. If a subject experiences more than 1 occurrence of a solicited event, the maximum duration of the events will be used. The time to first onset is defined as:

$$[\textit{date of first onset} - \textit{reference date} + 1]$$

The reference date is the start date of each vaccination period (ie, Post-dose 1 or Post-dose 2). Duration and time to onset of AEs will be expressed in days.

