9. STUDY EVALUATIONS

9.1. Study Procedures

9.1.1. Overview

The [Time and Events Schedule](#) summarizes the frequency and timing of safety, tolerability and immunogenicity measurements and evaluations applicable to this study. Details for all study procedures are provided in the following sections. Additional unscheduled study visits may be required if in the investigator's opinion, further clinical or laboratory evaluation is needed.

Visit Windows

The screening visit has to be performed within 8 weeks prior to the baseline visit (ie, the day of the subject's prime vaccination, Day 1). If a subject did not receive study vaccine on the planned day of vaccination, the timings of the next visits post-vaccination (see [Time and Events Schedule](#)) will be determined relative to the actual day of vaccination. Visit windows that

will be allowed are summarized in [Table 2](#). The subject should be encouraged to come on the exact day planned and use the visit window only if absolutely necessary.

Table 2: Visit Windows

| Visit description | Day | Window |
|--------------------------------|--|---------------|
| 7 Days Post-prime Vaccination | Day 8 for all groups | ±2 days |
| Boost Vaccination | Day 15 for Part 1 and Part 2, Group 2 Day 29 for Part 2, Group 1 | ±3 days |
| 7 Days Post-boost Vaccination | Day 22 for Part 1 and Part 2, Group 2 Day 36 for Part 1 and Part 2, Group 1 | ±2 days |
| 21 Days Post-boost Vaccination | Day 36 for Part 1 and Part 2, Group 2 Day 50 for Part 2, Group 1 | ±3 days |
| 42 Days Post-boost Vaccination | Day 57 for Part 1 and Part 2, Group 2 Day 71 for Part 2, Group 1 | ±3 days |
| Follow-up 6 Months Post-boost | Day 195 for Part 1 and Part 2, Group 2 Day 209 for Part 2, Group 1 | ±15 days |
| Follow-up 1 Year Post-boost | Day 380 for Part 1 and Part 2, Group 2 Day 394 for Part 2, Group 1 | ±30 days |

Blood Sampling Volumes

Approximately 571 to 675 mL of blood (including PBMC samples) will be drawn over a period of around 1 year, and remains well below the limits of standard blood donation. Additional blood may be drawn to confirm and follow-up on adverse events.

For details on the approximate blood sampling volumes collected by visit and the cumulative blood volumes, refer to the [Time and Events Schedule](#).

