1.5. Randomization and Blinding

Both Parts 1 and 2 of the study have completed randomization. Central randomization was implemented in this study. The randomization was used to minimize bias in the assignment of subjects to vaccination schedules (groups), to increase the likelihood that known and unknown subject attributes (eg, demographic and baseline characteristics) are evenly balanced across groups, and to enhance the validity of possible comparisons across groups. In addition, randomization was used to minimize bias in the assignment of subjects to study vaccine (active vaccine versus placebo). The randomization within each group was balanced by using randomly permuted blocks. There was stratification by age group (subjects ≥ 18 to ≤ 50 years versus subjects > 50 years).

For Part 1, subjects were randomized in a 4:1 ratio to either receive MVA-BN-Filo or placebo on Day 1 followed by a second vaccination with Ad26.ZEBOV or placebo 14 days later. Randomization was done separately for healthy subjects (N=50) and HIV-infected subjects (N=25).

For Part 2, subjects were randomly enrolled in 1 of 2 groups at study entry to either receive Ad26.ZEBOV,MVA-BN-Filo at day 1 and day 29 or MVA-BN-Filo, Ad26.ZEBOV at day 1 and day 15 in a 4:1 ratio (ie, Group 1 versus Group 2). Within each group, subjects were randomized in a 4:1 ratio to receive active vaccine versus placebo. Randomization was done separately for healthy subjects (N=250) and HIV-infected subjects (N=250). The start of randomization of HIV-infected subjects in Part 2 was contingent upon acceptable safety data from HIV-infected subjects from Part 1.

For each part, study-site personnel (except for those with primary responsibility for study vaccine preparation and dispensation, and not involved in any other study-related procedure), the sponsor (except for specifically designated sponsor personnel who are independent of the study) and subjects will remain blinded to the study vaccine allocation until the last subject in that part has completed at least the 6-month post second vaccination visit or discontinued earlier and the database has been locked for that part.

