Day 380 (365 days Post-dose 2)	[336; 396]	≥ 274	366
Day 394 (365 days Post-dose 2)			

^a The analysis based on the per protocol (PP) analysis set will be restricted to data points that fall within this window (ie, protocol-defined window).

^b The analysis based on the immunogenicity analysis set will be restricted to data points that fall within this window.

Note 1: The analysis windows and target days are based on the relative day (ie, with respect to reference day [day of dose 1 or dose 2 administration]).

Note 2: Day of dose 2 is also considered as Day 1 with respect to the second vaccination (ie, for calculating target days that fall after the second vaccination).

Note 3: Day 36, Day 57, Day 195 and Day 380 apply only to the 14-day interval vaccination schedule. While Day 50, Day 71, Day 209 and Day 394 apply only to the 28-day interval vaccination schedule.

Table 3: Analysis Periods

Phase	Period	Interval	
		From	To
Screening		00:00 on the date of signing the informed consent form	One minute prior to dose 1 administration on Day 1
Regimen*	Post-dose 1	Date and time of dose 1 administration	Minimum of: 
 a) 23:59 on the date of last contact (for early study discontinuation) b) 23:59 on the date of relative Day 29 Post-dose 1 c) 23:59 on planned visit day of dose 2 administration (in case dose 2 is not administered) d) one minute prior to dose 2 administration [□] e) 23:59 on the date of database cut-off (in case of interim analysis)
Post-dose 1 FU		One minute after the end of the Post-dose 1 period	Minimum of: 
 a) 23:59 on the date of last contact (for early study discontinuation or completion) b) one minute prior to dose 2 administration c) 23:59 on the date of database cut-off (in case of interim analysis)
Regimen*	Post-dose 2	Date and time of dose 2 administration	Minimum of: 
 a) 23:59 on the date of last contact (for early study discontinuation or completion) b) 23:59 on the date of relative Day 29 Post-dose 2 c) 23:59 on the date of database cut-off (in case of interim analysis) 
Note: subjects who do not receive dose 2 will not have a Post-dose 2 period.

Post-dose 2 FU		One minute after the end of the Post-dose 2 period	Minimum of: 
 a) 23:59 on the date of database cut-off (in case of interim analysis) b) 23:59 on the date of last contact (for early study discontinuation or completion)

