[□] For dose 2 administered earlier than Day 29 Post-dose 1 visit.

Note 1: * Regimen period includes both the Post-dose 1 and Post-dose 2 periods.

Note 2: FU = follow-up.

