7. SAFETY

The safety and tolerability data include the following:

- AEs (unsolicited AEs) collected from signing of the informed consent form (ICF) onwards until the 42-day Post-dose 2 visit.
- Serious adverse events (SAEs) and immediate reportable events (IREs) collected from signing of the ICF onwards until the end of the study.
- Solicited local and systemic AEs (reactogenicity) collected until 7 days after each administration of study vaccine.

The safety and tolerability data will be summarized based on the full analysis set. The analysis will be based on the actual dose (ie, dose 1 and dose 2 for the first and second vaccinations,

respectively) that the subjects received. For example, if dose 2 is not administered to a subject, then that subject will not be included in the analysis of AEs in the Post-dose 2 period. Focus will be on safety signals detected during the Post-dose 1 and Post-dose 2 periods, as well as the Regimen period (ie, combined Post-dose 1 and Post-dose 2 periods).

In general, safety data will be evaluated separately for each part of the study. Within each part, the data will primarily be presented by cohort (healthy and HIV-infected) and by vaccination schedule. Secondly, the data from Parts 1 and 2 of the study will be pooled (ie, 14-day interval regimen) and presented separately for the healthy and HIV-infected cohorts. See [Table 4](#) for a schematic overview the subgroups to be considered for the safety analysis.

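### Unsolicited-AE percentages for Post-dose 1 (about 14 vs 28 days) and Regimen (about 42 vs 56 days) should not be read across the two Part 2 schedules, and no common-window table is planned

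*SAP*

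**What the plan says.** - **Periods.** SAP Table 3 (section 2.1) ends Post-dose 1 at the earliest of several limits. Two of them are "23:59 on the date of relative Day 29 Post-dose 1" and "one minute prior to dose 2 administration". If dose 2 is not given, the planned dose 2 visit day is a further limit. Post-dose 2 runs to relative Day 29 after dose 2. Note 1 adds: "Regimen period includes both the Post-dose 1 and Post-dose 2 periods".
- **Dosing days.** Protocol Table 2 (section 9.1.1) places the boost at "Day 15 for Part 1 and Part 2, Group 2 Day 29 for Part 2, Group 1", each with a window of ±3 days.
- **Emphasis.** SAP 7 says: "Focus will be on safety signals detected during the Post-dose 1 and Post-dose 2 periods, as well as the Regimen period".
- **Display.** SAP 7.1.3 gives the general rule ("In general, the AEs following vaccination will be summarized (ie, tables of descriptive statistics) by vaccination schedule and presented per period/phase") and the statistic: "unsolicited AEs will be summarized (showing number and percentage) by System Organ Class (SOC) and Preferred Term (PT". Tables over the whole reporting period are limited to SAEs, fatal AEs, AEs that stop vaccination, Grade 3 AEs and IREs.
- **Allocation.** SAP 1.5: "For Part 2, subjects were randomly enrolled in 1 of 2 groups at study entry". The ratio is 4:1, 28-day to 14-day schedule. SAP 2.4 sets out the primary safety display as active against placebo within each part, cohort and dosing interval.

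**The concern.** A percentage of subjects with at least one event grows with the time over which events are counted. For two of the three focus periods, the SAP counts for 14 more days in the 28-day schedule than in the 14-day schedule, and it plans no table that equalises this.

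In Part 2 the two schedules are randomised against each other, so readers will naturally set the columns side by side. SAP 1.5 and Protocol 3.2 give valid comparison across groups as one reason for randomising. Protocol 11.4 leaves room for exploratory safety comparisons across groups of active subjects. A reader could see more unsolicited AEs in the 28-day schedule and attribute them to vaccine order or interval when the window length is the whole explanation.

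**Working it through.** **Period lengths.** The documents print no day counts for these periods; they follow from Table 3 and the dosing days.

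| Period | 14-day schedule | 28-day schedule |
|---|---|---|
| Post-dose 1 | 15 − 1 = 14 | 29 − 1 = 28 |
| Post-dose 2 | 28 | 28 |
| Regimen | 14 + 28 = 42 | 28 + 28 = 56 |

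With dose 2 anywhere in its ±3-day window, Post-dose 1 is 11 to 17 days against 25 to about 29 (the Day 29 cap). The ranges do not overlap. A missed dose 2 does not remove the difference, because the planned dose 2 day also depends on the schedule.

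**Size when the schedules truly do not differ.** The documents give no background rate for unsolicited AEs, so the base risks are assumptions. Let H(D) be the hazard accumulated D days after a dose: H(D) = D if constant, or 1 − 0.5^(D/h) if it halves every h days and restarts at each dose.

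*Post-dose 1, assuming 10% over 14 days.* The 28-day figure is 1 − 0.9^k with k = H(28)/H(14).
- Constant: k = 28/14 = 2, giving 19.0%.
- h = 7: k = 0.9375/0.75 = 1.25, giving 12.3%.
- h = 3: k = 1.039, giving 10.4%.

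*Regimen, assuming 20% over 42 days.* The 56-day figure is 1 − 0.8^k with k = 2H(28)/(H(14) + H(28)).
- Constant: k = 56/42 = 1.333, giving 25.7%.
- h = 7: k = 1.111, giving 22.0%.
- h = 3: k = 1.019, giving 20.3%.
- h = 7, with the dose 1 hazard continuing past dose 2: k = (H(56) + H(28))/(H(42) + H(28)) = 1.006, giving 20.1%.

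The gap from a 20% base is thus 0.1 to 5.7 points. It moves with the base. Under a constant hazard, 1 − 0.95^(4/3) = 6.6% (gap 1.6 points at 5%) and 1 − 0.5^(4/3) = 60.3% (gap 10.3 points at 50%).

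The 10% and 20% bases are separate illustrations. Under a constant hazard, 10% over 14 days implies 1 − 0.9³ = 27.1% over 42 days and 1 − 0.9⁴ = 34.4% over 56 days.

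**Exposure-adjusted rates.** The Regimen rate ratio, 28-day to 14-day schedule, is k × 42/56 = 1.00 (constant), 0.83 (h = 7) or 0.76 (h = 3), again with no true difference.

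**Check of the remedy.** With Post-dose 1 cut at 14 days in both schedules and Post-dose 2 kept at 28, Regimen is 42 days in both, and equal hazards give equal percentages. The worst early case has every dose 2 in the 14-day schedule on Day 12. Under a constant hazard this leaves Post-dose 1 at 1 − 0.9^(11/14) = 7.9% against 10.0%, and Regimen at 1 − 0.8^(39/42) = 18.7% against 20.0%. An 11-day cut in both schedules removes that gap.

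**The case against.** **No planned comparison is affected.** The study is descriptive. Its only comparative safety objective is healthy against HIV-infected, within schedules that share the same windows. Protocol 11.4 leaves exploratory comparisons to be described in the SAP, and its example is again healthy against HIV-infected on a similar regimen. The SAP describes no safety contrast between schedules. This stands, and it limits the weight of the point.

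**Placebo already guards against misreading.** Each schedule has concurrent placebo subjects observed over the same window, so a rise caused by window length should appear there too. This stands in part. The 14-day schedule has only 10 placebo subjects per Part 2 cohort, so one subject moves that percentage by 10 points.

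**The larger figures need a constant hazard.** If events cluster after doses, the Regimen gap from a 20% base is 0.1 to 2.0 points. Both schedules also have the same scheduled safety-laboratory draws after dose 1 (Day 8 and the dose 2 visit, before injection). For AEs found only by those draws, the extra 14 days add no scheduled opportunity for detection. This stands too: the constant-hazard figures suit background illness and overstate the effect for laboratory findings.

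**Stronger readings the documents do not support.** A reader might infer that the trial's between-schedule safety conclusions are biased in general. They are not: Post-dose 2 is 28 days in both schedules, and solicited AEs are collected for 7 days after each dose. A reader might also infer that the tables pooled by vaccine mix unequal windows. The wording leaves open whether dose positions are combined, and SAP Table 4 lists no safety pooling across intervals, so that is speculation.

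**Conclusion.** The point holds within a narrow scope. The 14 vs 28 and 42 vs 56 day windows follow directly from SAP Table 3 and the dosing days, and no planned table puts Post-dose 1 or Regimen unsolicited AEs on a common window. The percentages properly describe each regimen as given. They should not be read across the two randomised schedules.

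The size is uncertain. It rests on assumed base risks and on event timing, and ranges from negligible for tightly clustered events to nearly double for Post-dose 1 under a constant hazard. Active against placebo, and healthy against HIV-infected, remain sound within a schedule. No formal test or SAP-specified contrast changes. This is a worthwhile, inexpensive improvement to how the tables can be read; it does not invalidate the safety analysis.

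**What to change.** In SAP 7.1.3:

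1. Keep all planned tables and footnote the Post-dose 1 and Regimen lengths by schedule.
2. Add one unsolicited-AE table for Part 2 by schedule. Cut Post-dose 1 to the same length in both schedules, keep Post-dose 2 at 28 days, and define Regimen as the two together. Choose the cut in advance: either 14 days, censored at dose 2, or 11 days, so that everyone dosed within the ±3-day window is fully observed.
3. Exposure-adjusted rates may be added as a supplement, with a note that they favour the longer schedule if events cluster after doses.

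**Cost.** SAP wording, footnotes and one table from data already collected.

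**Downsides.** The added table drops dose 1 events after the cut. With the 14-day cut, the 28-day schedule loses 14 of its 56 Regimen days. With the 11-day cut it loses 17 of 56, and the 14-day schedule loses 3 of 42. The 14-day version can leave a small gap when dose 2 is early. It can also catch the pre-dose 2 laboratory draw in the 14-day schedule (Day 15) but not in the 28-day schedule (Day 29), which matters for AEs dated to that draw. The 11-day version largely avoids both.
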